7.3.4 Other Sets

Not applicable.

7.4 Covariates and Subgroups

There are no plans to adjust the primary efficacy analysis for baseline characteristics and disease status. Exploratory analyses will be conducted to assess the potential contribution of baseline disease characteristics on the likelihood of a response to treatment.

Exploratory analyses will be performed to assess the potential impact of various prognostic factors on efficacy. Appropriate statistical models will be fit with these factors as covariates and the effect of treatment will be assessed after adjusting for other significant risk factors. Risk factors will include, but are not limited to age, gender, region, and baseline EZ area.

7.5 Out of Window Visits for Primary and Secondary Variables

Every effort will be made to keep missing data at a minimum. Due to COVID-19, participants may not be able to attend their scheduled study visits within the protocol-specified visit window (+/- 30 days). To accommodate such delays, efficacy assessment visits delayed due to COVID-19 but conducted within -30 days of Month 12 visit or +119 days of the planned visit timepoints for Months 12, 16, 20, and 24 will be included in the analysis. To account for the variable timing of visits, the relative study day of assessments will be included in regression models as a continuous measure of Time where relative study day is defined as the number of days since surgery.

If time is included as a categorical variable (see Section 7.6), an estimated value for the scheduled visit endpoint will be computed from the raw data, adjusting the observed value to an estimated value at the targeted visit time, based on a linear trend since the previous observation. The estimated value for a participant-visit will be computed by determining the linear slope between the previous visit and the current visit. The estimated value will be the fitted value to that line at the targeted timepoint.

7.6 Interim Analyses

No formal interim analyses or early unmasking are planned.

Prior to the completion of the study and database lock, summaries of the distribution of timing of efficacy visits (excluding any efficacy variables themselves) will be compared between treatment arms to determine if the pattern of visit attendance is comparable between treatment arms.

In addition, masked summaries of the overall results will be analyzed to determine appropriate parameterization of time as a continuous or categorical variable for the primary efficacy analysis. The determination of non-linearity will be concluded if the observed pattern of EZ area loss response over time follows a distinctly non-linear trend. Assessment will be made through an overall linear regression goodness-of-fit analysis, including review of a residual plot from a simple linear regression.

The analysis will be limited in scope and will not reveal unmasked results. No type I error adjustment will be made.

7.7 Data and Safety Monitoring Committee

An independent DSMC will be established to monitor safety and the study conduct and will meet to review masked safety summaries prepared by the Coordinating Center. Members of the DSMC are external to the Sponsor and will follow a charter that outlines its roles and responsibilities. No interim analysis for efficacy is planned for this study.

The DSMC will review accumulating data for safety per the DSMC Charter. The DSMC will be responsible for monitoring data and safety and will exercise oversight of the clinical investigation independently from the study investigators. In addition, the DSMC will be responsible for reviewing the study design and, as appropriate, recommending safety design changes. More details on the DSMC role and responsibility for data monitoring can be found in the Charter.

Participants will be monitored during all study visits for AEs by the study investigators. The investigator will be responsible for the appropriate medical management of all AEs and for the personal safety and well-being of the participants. In case of an AE, the clinical investigator will initiate appropriate treatment per his/her medical judgment and will decide whether to continue treatment through full resolution of the event, discontinue the IP, or withdraw the participant from the study.

Regardless of severity or relationship to the IP, all AEs occurring during the study will be recorded in the participant's CRF. Any SAE will be reported immediately by entering the data into the EDC system within 24 hours of the investigator becoming aware of the occurrence of a serious or unexpected AE. This will notify the Coordinating Center which in turn will notify the Sponsor.

7.8 Multiple Comparisons/Multiplicity

The primary efficacy analysis involves a single hypothesis test at the 2-sided significance level of 5%. A hierarchical testing procedure will be applied to secondary efficacy analyses to control the overall type I error rate. In the case that the primary efficacy analysis is statistically significant, the secondary efficacy endpoints will be tested at a 2-sided type I error rate of 0.05 in the order listed below. If any of the secondary endpoints are found to be not statistically significant at the 2-sided 0.05 level, the hypothesis testing will stop. Later endpoint(s) will be summarized descriptively and p-values may be produced for descriptive purposes only.

- Mean change in aggregate sensitivity of microperimetry within the EZ line break area from the Baseline Visit through the Month 24 Visit
- Mean change in reading speed from the Baseline Visit through the Month 24 Visit

- Mean change in the National Eye Institute Visual Function Questionnaire-25 (NEI-VFQ-25) near activities subscale score from the Baseline Visit through the Month 24 Visit

P-values produced for safety analyses and treatment group comparisons of demographic and baseline characteristics will be considered descriptive statistics that support the results of the primary efficacy analysis and not as formal tests of hypotheses.

8 STUDY PARTICIPANTS

8.1 Disposition of Participants

Number and percentage of participants in the following categories will be summarized as appropriate:

- Randomized and received surgery (FAS)
- Randomized, Received Surgery and at least one safety measurement (Safety Set)
- Included in the PPS
- Prematurely discontinued in the study during the Treatment or Extension Periods and the reasons for discontinuations

A time to premature discontinuation analysis using the Kaplan-Meier method will be provided to assess the comparability of treatment groups in terms of premature discontinuation.

The disposition summary and discontinuation analysis will be based on the mITT Population.

8.1 Demographics and Baseline Characteristics

Demographic and ocular baseline characteristics (e.g., baseline EZ area) will be summarized. The demographics and baseline characteristics will be presented for both the mITT Population and the PP Population to allow review of characteristics of those included in the efficacy analysis, which will be based on these populations.

The medical and ophthalmic history data will be collected at the baseline visit including:

- Ongoing medical conditions
- Ocular history, ongoing ocular history, and confirmation of MacTel

Medical and ophthalmic history conditions will not be coded using the Medical Dictionary for Regulatory Activities (MedDRA). Therefore, there will be no summary table, but all conditions will be provided in a participant listing for the FAS only.

8.2 Protocol Deviations

Protocol deviations will be provided as a participant data listing only. Major protocol violations will also be identified for analysis purposes.

8.2.1 Prior and Concomitant Medications

Frequency distributions and listings of concomitant medications will be shown by Anatomical Therapeutic Chemical (ATC) drug classification, drug name and treatment group. The medications will be shown separately for those starting before and after implant/sham surgery. All concomitant medications will be coded using the World Health Organization Drug Dictionary (WHO-DD). Prior and

concomitant medications will be summarized for the Safety population.

If medication start date is on or after date of dosing of study drug, then medication will be summarized as a concomitant medication regardless of whether medication end date is missing or not. If medication end date is before date of surgery, then medication will be summarized as prior medication regardless of whether medication start date is missing or not. Note that medication that started prior to surgery and continued after surgery will be summarized as prior medication and separately as a concomitant medication. Both prior and concomitant medications will be based on the FAS. If the data contain missing or partial medication start and stop dates which do not allow definitive classification as either a prior medication, concomitant medication, or both, a conservative rule will be implemented. This will be detailed in the statistical programming document for the study.

8.2.2 IP Exposure

IP for this study is the NT-501 implant that remains in place for the duration of the study, therefore the participant is not responsible for administering IP. An analysis of IP compliance is not measured, yet information will be provided on the number and percentage of participants based on the mITT Population who have the device removed during the study period.

9 EFFICACY EVALUATION

9.1 Primary Efficacy Analysis

The primary hypothesis is that the NT-501 implant will slow the rate of change in the EZ (IS/OS) area loss. The primary efficacy endpoint will be analyzed using the mITT Population but restricted to only those participants with at least 3 visits recorded: Baseline, Month 24, and at least one of Month 12, 16, or 20 visits. An analysis will also be conducted with the PP Population with the same restriction to only participants with at least 3 visits recorded: Baseline, Month 24, and at least one of Month 12, 16, or 20 visits.

The primary efficacy variable will be the rate of change that will be determined by using values from the EZ area as measured by SD-OCT. EZ area will be defined as the mean of 2 independent readings of the single eligible SD-OCT enface image taken at Baseline and at Months 12, 16, 20, and 24. A longitudinal mixed model will include EZ area as the dependent variable, a random intercept term to account for within subject variability, treatment group, time as a continuous variable, and the interaction between treatment and time. Time will be captured as the relative study day of the respective efficacy assessment and will include the days corresponding to the Baseline, Month 12, 16, 20, and 24 visits. The difference in the rate of change in EZ area over 24 months will be computed by including Baseline, Months 12, 16, 20, and 24 EZ measurements, will be compared using a random intercept model and the corresponding 95% confidence interval (CI), SE, test statistic, and 2-sided p-value of the difference between treatment group parameters by computing the parameter estimate for the treatment by time interaction term. An unstructured covariance structure will be implemented as with continuous time there will be a single parameter each for between and within participant variability.

Prior to the analysis, out of window visits will be incorporated as noted in Section 7.5. With a mixed effects model as the primary analysis model, no imputation of missing data will be done.

As stated in Section 7.6, it may be determined prior to study end and database lock that the most appropriate parameterization of time is as a categorical variable. If this occurs, the modification to the

above plan will be documented ahead of analysis. The model will proceed as described above with the exception that time will be included in the model with nominal visit labels for Months 12, 16, 20, and 24. The comparison between treatment groups will be assessed at Month 24. The preferred covariance structure is Unstructured. If the model does not converge, the covariance structure will be selected from one of the following: Variance Component, Compound Symmetry, or Auto-regressive covariance matrix through comparison of the Akaike Information Criterion [17].

9.2 Secondary Efficacy Analysis

The secondary endpoints will be analyzed using the mITT Population and the PP Population to test for superiority of NT-501 implant over sham. The secondary endpoints are listed below:

- Mean change in aggregate sensitivity of microperimetry within the EZ line break area from the Baseline Visit to the Month 24 Visit
- Mean change in reading speed from the Baseline Visit to the Month 24 Visit
- Mean change in the National Eye Institute Visual Function Questionnaire-25 (NEI-VFQ-25) near activities subscale score from the Baseline Visit to the Month 24 Visit

The observed change from Baseline visit to the Month-24 visit will be compared using t-tests. The analyses will be based on the actual values observed at the Baseline and the Month-24 visit efficacy assessment, regardless of timing of the visit as long as it occurs within +/- 30 days for pre-COVID period or within +119 days post-visit timepoint for COVID-related delays. The estimated mean treatment effect, a 95% confidence interval (CI), and a 2-sided p-value will be provided. No imputation of missing data will be done.

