## 12. STATISTICS

### 12.1 GENERAL PROCEDURES

This is a Phase 3 study to evaluate the efficacy and safety of NT-501 compared with the sham procedure for the treatment of MacTel.

One eligible study eye from each participant will be randomized in a 1:1 ratio as follows:

- Surgery to receive 1 NT-501 device implant delivering a nominal CNTF dose of 20 ng/device/day
- Sham surgery

Randomization: Two treatment assignments with a 1:1 (NT-501 surgery: sham procedure) allocation scheme for each of the 2 protocols (Protocol A and Protocol B). The actual treatment assignment (NT-501 surgery or sham procedure) will be shown within Advantage eClinical. Randomization is unrestricted. One randomization list per protocol will be generated. There will be no stratification for prognostic factors.

The biostatistician will prepare detailed statistical procedures, listings, table shells and figures in a separate statistical analysis plan (SAP). The following key components will be considered, and a detailed description will be documented in the SAP:

- Descriptions of primary and secondary endpoints and how they will be measured
- Statistical methods and any applicable alternative methods (eg, model nonconvergence) used to analyze the endpoints
- Justifications for sample size calculations
- Multiple testing approaches
- Approaches to account for missing data

A biostatistician will perform statistical analyses as agreed with the sponsor according to the SAP. Any additional or supplemental data analyses performed independently by an investigator shall be submitted to the sponsor for review.

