### 12.3.2 Secondary Endpoint(s)

The secondary endpoints will be analyzed using the mITT population and the PP population to test for superiority of NT-501 over sham. The secondary endpoints are listed below:

- Mean change in aggregate sensitivity of microperimetry within the EZ line break area through 24 months
- Mean change in reading speed from baseline through 24 months
- Mean change in the NEI-VFQ-25 near activities subscale score from baseline through 24 months

Continuous secondary outcomes will be analyzed using a longitudinal mixed effects model and the corresponding 95% CI, SE, test statistic, and p-value of the difference between treatment group means at the 24-month time point will be computed. For the mixed effects model, fixed effects will include the treatment group (between-participant factor) and the visit (within-participant factor). The unstructured covariance matrix is preferred for this analysis. If the model does not converge, the “best” covariance structure will be chosen based on Akaike’s Information Criteria.

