### 12.3.3 Analysis of Safety

Safety analyses will be performed on all participants who underwent either implant surgery or the sham procedure. The assessment of safety will be based on the summary of ocular and nonocular treatment-emergent AEs (TEAEs) and ophthalmic examinations. The Medical Dictionary for Regulatory Activities (MedDRA) nomenclature will be used to code AEs.

The TEAEs will be presented by treatment group (NT-501 versus sham). Summaries for TEAEs include the following: all TEAEs regardless of causality, treatment-related TEAEs, ocular TEAEs, treatment-related ocular TEAEs, TEAEs by intensity, SAEs, and TEAEs leading to discontinuation from the study.

The number and proportion of participants with a loss in BCVA of 15 or more letters from baseline in the study eye will be tabulated and presented by treatment group.

Detailed methods for the analysis of all endpoints will be outlined in the SAP.

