9.2.1 Sensitivity Analysis of Secondary Endpoints

- Exclusion of out of window visits: An analysis will be conducted excluding any out of window visits occurring more than +/- 30 days outside of the planned timepoints. Time-adjusted analysis: Time-adjusted analysis will be performed by adjusting the actual efficacy assessment results to the nominal timepoint, as described in Section 7.5.

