12 SUMMARY OF CHANGES IN THE CONDUCT OF THE STUDY OR PLANNED ANALYSES

No changes in the conduct of the study or planned analyses will be applied at this time.

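### The SAP names two different tests, t-test in Section 9.2 and MMRM in Appendix B, for the same three hierarchy-controlled secondary endpoints and does not say which is confirmatory

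*SAP*

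**What the plan says.** - SAP 9.2, covering the three secondary efficacy endpoints: "The observed change from Baseline visit to the Month-24 visit will be compared using t-tests". The section also gives the populations, the visit windows, a 95% confidence interval, a two-sided p-value and no imputation.
- SAP Appendix B gives MMRM as the analysis model in all three secondary rows, with populations FAS and PPS. It states no model terms, covariance structure or contrast.
- SAP 9.2.1 lists two sensitivity analyses: exclusion of out-of-window visits, and a time adjustment ("Time-adjusted analysis will be performed by adjusting the actual efficacy assessment results to the nominal timepoint, as described in Section 7.5"). MMRM is not among them.
- SAP 7.8 puts the three endpoints in a fixed order at two-sided 0.05, after a significant primary result, and names no test: "If any of the secondary endpoints are found to be not statistically significant at the 2-sided 0.05 level, the hypothesis testing will stop".
- Protocol 12.3.2: "Continuous secondary outcomes will be analyzed using a longitudinal mixed effects model", from which the "difference between treatment group means at the 24-month time point will be computed". The fixed effects it lists are treatment group and visit.
- Protocol 12.1 and 12.3.3 leave the detail to the SAP: "A biostatistician will perform statistical analyses as agreed with the sponsor according to the SAP" and "Detailed methods for the analysis of all endpoints will be outlined in the SAP".
- SAP 12: "No changes in the conduct of the study or planned analyses will be applied at this time". SAP 6.1 records other modifications only and mentions no change of secondary test.

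**The concern.** A fixed sequence controls error only if the test at each step is settled in advance. Here one SAP offers two candidates for each of three steps. The method used for microperimetry decides whether reading speed, and then near activities, may be formally tested at all.

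The SAP's own safeguards may not catch a switch. The Preface requires deviations from analyses described in the SAP to be noted, and SAP 9.3 labels analyses that the SAP did not identify. Both methods appear in the SAP, so a report based on either could be presented as planned.

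What is at stake is whether the secondary claims count as confirmatory. The validity of either test is not in doubt.

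**Working it through.** **The plan's own figure.** No power or error figure is given for the secondary endpoints. The only sample-size figure is for the primary: 2(1.960 + 0.842)² × 0.0256 × (1 − 0.6) / (5 × 0.47 × 0.037²) = 49.97, so 50 per group, as stated. It does not bear on this point, except that the increase from 50 to 56 gives an upper missing-data case of 6/56 = 10.7%.

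**Measure used.** Let Z1 be the t statistic and Z2 the mixed-model statistic, with correlation r under the null. The error rate if either could be claimed is P(|Z1| > 1.96 or |Z2| > 1.96), from the bivariate normal distribution. When one estimator is efficient relative to the other, r is the square root of their variance ratio. The documents give no correlations, SD ratios or missing rates for these endpoints, so those below are assumptions.

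**Case A: MMRM of change with treatment-by-visit and no baseline covariate** (neither choice is stated for these endpoints). With complete data the Month-24 difference equals that of the t-test. With a fraction p of Month-24 values missing at random, the MMRM also uses the m earlier changes.
- Under exchangeable raw correlation ρ, two change scores have covariance σ²(1 − ρ) and variance 2σ²(1 − ρ), so they correlate 0.5 whatever ρ is.
- R² of the Month-24 change on m earlier changes = 0.25m / (1 + 0.5(m − 1)). This is 0.25 for m = 1 (reading speed and near activities, Month 12) and 0.40 for m = 4 (microperimetry, Months 6, 12, 16, 20), per SAP Appendix A.
- Variance ratio MMRM / t-test = 1 − pR².

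| p | ratio, m = 1 | either, m = 1 | ratio, m = 4 | either, m = 4 |
|---|---|---|---|---|
| 2% | 0.995 | 0.0533 | 0.992 | 0.0542 |
| 5% | 0.9875 | 0.0552 | 0.980 | 0.0566 |
| 10.7% | 0.973 | 0.0576 | 0.957 | 0.0597 |

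The Protocol's Schedule of Events also marks Months 16 and 20 for reading speed and the questionnaire, although its visit-by-visit sections do not. With m = 3 the figures are 0.0540, 0.0564 and 0.0593, inside the same range.

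Simulation (40,000 runs each, 56 per arm, ρ = 0.6) with 1, 3 and 6 missing per arm gives 0.0536, 0.0536, 0.0581 (m = 1) and 0.0528, 0.0556, 0.0592 (m = 4). Each test alone gives 0.048 to 0.051. The Monte Carlo standard error is about 0.001, so the split by m means nothing at the lowest rate.

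If correlation instead decays over time (AR(1), baseline-to-Month-24 correlation 0.6 or 0.8), the figures are about 0.057 to 0.059 at 5% missing and 0.060 to 0.064 at 10.7%.

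If the t-test has 80% power, the two methods reach different conclusions in 1.6% to 2.0%, 2.5% to 3.2% and 3.7% to 4.7% of trials at the three missing rates (exchangeable case).

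**Case B: only the fixed effects listed in Protocol 12.3.2** (treatment and visit), change as response, compound symmetry, complete data. The treatment coefficient is then an average over K visits, and r = √[(1 + 1/K)/2].
- K = 2 (Months 12, 24): r = 0.866, either = 0.073.
- K = 5 (Months 6 to 24): r = 0.775, either = 0.080.
- For an effect growing linearly, this coefficient targets (12 + 24)/(2 × 24) = 0.75 or (6 + 12 + 16 + 20 + 24)/(5 × 24) = 0.65 of the Month-24 difference. Where the t-test has 80% power, it has about 68% or 65%.

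**Case C: mixed model or ANCOVA with a baseline covariate**, complete data. With equal variances the variance ratio is (1 + ρ)/2.
- ρ = 0.4, 0.6, 0.8: ratio 0.70, 0.80, 0.90; either = 0.076, 0.071, 0.065.
- With Month-24/baseline SD ratio k, the variance ratio is k²(1 − ρ²)/(1 + k² − 2ρk). Over k = 0.8 to 1.2 and the same ρ it runs from 0.538 to 0.997, and either from 0.082 to 0.053.

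**The case against.** The best defence is that Section 9.2 is the operative text. It alone can be programmed as written. Appendix B is an overview, gives a bare model name, and uses a population label (FAS) that SAP 7.3 does not define, so it may be a leftover. On that view, replacing the t-test by MMRM would depart from described text, and the Preface would require it to be noted. This is a fair reading and lowers the severity. It does not close the gap: the SAP nowhere says that Section 9.2 prevails, and MMRM matches the protocol's model, so a reader could equally take the appendix as the intended plan.

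A second defence is that error inflation is limited. This stands. Each test holds its level, and because the secondaries are tested only after a significant primary result, familywise error under the global null stays at 0.05.

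A reader might also infer that the SAP departs from Protocol 12.3.2 without declaring it. The documents do not establish that. The protocol defers detailed methods to the SAP. The SAP also appears to predate Protocol 7.0: SAP 6.1 refers to amendment 5, and SAP 4.1 still plans Month-36 and Month-48 follow-up to a common end around August 2022, whereas Protocol 4.1 discontinues those visits. The protocol text in force when the SAP was written is not available.

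**Conclusion.** The inconsistency is real and lies within the SAP: t-test in Section 9.2, MMRM in Appendix B, no ranking, and no sensitivity label for MMRM. The confirmatory test at each secondary step is therefore not uniquely pre-specified. The mismatch with Protocol 12.3.2 is something to align.

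The size depends on which mixed model is meant, and the documents do not settle that. Case A gives no difference with complete data and about 0.053 to 0.060 under exchangeable correlation with 2% to 10.7% missing. Case B gives about 0.073 to 0.080 even with complete data. Case C gives about 0.065 to 0.076 with equal variances. These figures illustrate what would follow if either result could be claimed. Nothing in the documents suggests that a choice was or will be made after unmasking, and Protocol 12.1 expects missing data to be minimal.

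This should be fixed. It matters because of the tests' role in the hierarchy, not because of a large error inflation.

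**What to change.** Before database lock:
- Name one confirmatory method and its Month-24 contrast in the mITT population, and state it identically in SAP 9.2 and Appendix B. Replace FAS in the appendix with mITT; SAP 8.1 describes FAS as the same set (randomized and received surgery).
- List the other method as a sensitivity analysis in SAP 9.2.1.
- Align Protocol 12.3.2, or note the difference in SAP 12.
- If MMRM is chosen, state treatment, visit and treatment-by-visit as fixed effects, so that the contrast is the Month-24 difference.

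The choice between the methods is the sponsor's.

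A separate, optional improvement is to adjust the chosen analysis for the endpoint's baseline value (ANCOVA if only two time points are used). With equal variances this cuts the variance of the treatment difference by 1 − (1 + ρ)/2, which is 10% to 30% for assumed correlation 0.8 to 0.4. With SD ratios of 0.8 to 1.2 the cut ranges from 0.3% to 46%.

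The cost is document wording and routine programming. Baseline values are already collected, so no new data are needed.
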